5.0 Procedures Involved*

Enrollment Procedures. Enrollment in this study may occur at any time during the recruitment period. Potential participants recruited utilizing the OneFlorida Data Trust will receive a “text-in” number, in which interested persons will be able to text-in to receive instructions for screening and enrollment. Potential participants through the OneFlorida Data Trust who do not “opt-out” of being contacted could also be directly contacted by the study team to be informed of the study and screening/enrollment options for preliminary eligibility.

Screening and enrollment may occur on the same day, as long as the appropriate VL and ART regimen data are appropriately obtained. If a participant is determined to be eligible for the study, a unique Qualtrics link will be sent to the participant for submitting proof of HIV VL ≥ 200 copies/mL and ART regimen. After final eligibility is determined, study staff sends the potential participant the SMART enrollment link, which contains the study

PROTOCOL TITLE: ATN 144 SMART

consent/assent form, HIPAA Authorization form, and the baseline web-based survey. These are programmed in Qualtrics by the REC. The baseline survey can be completed at the participant's convenience (ideally within 14 days before and 28 days after their scheduled assessment date). Upon completion of all portions of the enrollment link, participants are considered enrolled in SMART. Study staff will then randomize and stratify the participants into their respective intervention arms (CPS or SMS) for the first period of the study. Stratification is based on method of contraction: Perinatal vs Behavioral (and other).

Participants randomized to the CPS intervention group will speak with the AF to determine the start day and call time for intervention phone calls. This phone call should be completed within 30 days from entry. Participants randomized to the SMS intervention will speak with the Project Coordinator (PC) to identify the start day, timing, and content of the text messages they will begin receiving daily.

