At each follow-up, participants will complete web-based surveys programmed in Qualtrics by the REC. A link to these computerized surveys will be sent to each participant by the REC and can be completed at the participant's convenience (ideally within 14 days before and 28 days after their scheduled assessment date). Participant VL data will need to be obtained before the study procedures for the respective assessment period is considered complete and the participant is compensated. Data files will be downloaded via Qualtrics by the Data Management Team of the REC. The REC will maintain a linkage of PID and subject name, and these will be stored in password protected files. These web-based surveys will take approximately 60-90 minutes to complete.

Randomization Process/Systems. Participants will be randomized at the end of their baseline assessment into one of two intervention conditions: (1) CPS or (2) SMS. Both intervention conditions will receive 3 months of intervention (i.e., 3 months of CPS or SMS). Each participant's condition will be tracked in REDCap. At the 3-month follow-up, a second stratified randomization will occur in blocks with 8 possible intervention trajectories as follows:

- CPS responders (VL <200 copies/mL) will be randomized to either 9 months of standard care (SC) or 3 months of CPS-T followed by 6 months of SC;
- CPS non-responders (VL \geq 200 copies/mL) will be randomized to 3 months of CPS-I or SMS-I followed by 3 months of CPS-T or SMS-T, respectively, and then 3 months of SC for both groups thereafter;
- SMS responders (VL <200 copies/mL) will be randomized to either 9 months of SC or 3 months of SMS-T followed by 6 months of SC; and
- SMS non-responders (VL \geq 200 copies/mL) will be randomized to 3 months of CPS-I or SMS-I followed by 3 months of CPS-T or SMS-T, respectively, and then 3 months of SC for both groups thereafter.

Participants who are unable to provide a valid HIV VL result at the 3-month time point have approximately 30 days to obtain a HIV VL performed at Quest Diagnostics or have a physician release this information to PRIDE. Participants who are unable to provide this

PROTOCOL TITLE: ATN 144 SMART

information within the timeframe i.e. 30 days after their 3 month follow-up assessment will be treated as non-responders to the intervention and will be re-randomized to an incentive arm. The 30 day window follows the same timeframe as the 30 day window for calls to begin following baseline.

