16.0 Data Management* and Confidentiality

Data Management and Data Quality. The first randomization involves allocation to CPS vs. SMS using a 1:1 allocation ratio. This step will use stratified randomization in permuted blocks to achieve balance in distribution of behaviorally and perinatally infected youth. The REC data team will program the randomizer in Qualtrics and will not participate either in the intervention delivery or in the adherence reinforcement steps. The protocol team will monitor race, ethnicity, and gender to ensure balanced distribution at the first stage. After 6 months, stratified randomization will occur with permuted blocks within each trajectory. Since second stage randomization is dependent on first stage response status, we will only maintain the balance within each first stage treatment outcome when randomizing at the second stage.

Following the Analytic Core's (AC) standard quality assurance, including checking for outliers and abnormal values using graphical methods, we will verify that the distributions of measures meet the assumptions of the statistical tests to be used, applying a formal test such as the Shapiro-Wilk's test [60]. Transformations will be used when distributional assumptions are not fulfilled. Tests will be conducted to identify potential relationships among baseline demographic and clinical variables and our dependent variables and to see whether they are balanced between groups. If a baseline variable is not balanced between groups and is correlated with the dependent variable ($r > .30$), we will include this variable as a covariate in subsequent analyses. Since we will test more than one primary hypothesis with one primary outcome variable (VL suppression), the Hochberg step-up multiplicity adjustment will be used with a two-tailed family wise alpha-level of .05 [61]. All other tests described below will each have a two-tailed alpha-level of 0.05. Outcome analyses will be based on the principle of intention-to-treat [62].

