1.1 Data Management and Data Quality

The first randomization involves allocation to CPS vs. SMS using a 1:1 allocation ratio. This step will use stratified randomization in permuted blocks to achieve balance in distribution of behaviorally and perinatally infected youth. The REC data team will program the randomizer in Qualtrics and will not participate either in the intervention delivery or in the adherence reinforcement steps. The protocol team will monitor race, ethnicity, and gender to ensure balanced distribution at the first stage. After 6 months, stratified randomization will occur with permuted blocks within each trajectory. Since second stage randomization is dependent on first stage response status, we will only maintain the balance within each first stage treatment outcome when randomizing at the second stage.

Following the Analytic Core's (AC) standard quality assurance, including checking for outliers and abnormal values using graphical methods, we will verify that the distributions of measures meet the assumptions of the statistical tests to be used, applying a formal test such as the Shapiro-Wilk's test [60]. Transformations will be used when distributional assumptions are not fulfilled. Tests will be conducted to identify potential relationships among baseline demographic and clinical variables and our dependent variables and to see whether they are balanced between groups. If a baseline variable is not balanced between groups and is correlated with the dependent variable ($r > .30$), we will include this variable as a covariate in subsequent analyses. Since we will test more than one primary hypothesis with one primary outcome variable (VL suppression), the Hochberg step-up multiplicity adjustment will be used with a two-tailed family wise alpha-level of .05 [61]. All other tests described below will each have a two-tailed alpha-level of 0.05. Outcome analyses will be based on the principle of intention-to-treat [62].

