1.2.1 Primary Analysis Plan

The primary analysis will be a comparison of SRA (primary outcome) between the CPS and the SMS group at the end of first stage of randomization. This will be performed using a χ^2 test. We will also compare the VL suppression between the two groups for those available subjects, albeit this is no longer treated as primary outcome. Since SRA (and VL) is a continuous measure, we will use two-sample t-test to conduct this analysis. We will also compare the self-reported medication adherence rate (secondary outcome) between the two groups using a χ^2 test. All the primary analyses will be based on initial assignment to groups, using the ITT principle. Each of the primary hypotheses will be tested using linear mixed-effects (LME) regression analyses.¹⁰⁴ For testing primary hypothesis 1 (PH1), the model will include up to 3 repeated assessments of VL suppression (weeks 0/baseline, 12, 24, 36, 48). For primary hypothesis 2 (PH2), we will only focus on non-responders (for both CPS and SMS at stage 1) and compare the SRA as dependent variable using a repeated measure LME (weeks 0/baseline, 12, 24, 36, 48). In an effort to get the outcome for PH2 some subject may have final outcome at latter date than 48 weeks. Each LME model will include a random intercept and slope and fixed effects for adherence intervention group, and time, as well as the stratification variables: clinical site, age, gender. A likelihood ratio test will examine the incremental contribution of the group by time interaction, which represents the interaction of interest for PH1 and PH2, testing for a differential adherence intervention effect over time. The decision rule for each primary hypothesis calls for rejection of H_0 if this interaction is statistically significant using the Hochberg adjustment. A site by group interaction will be also examined and included in each model (above) if significant at the 0.05 level. The purpose of the LME based analysis for the primary aim is to determine which of the first-stage intervention, CPS or SMS, is associated with the most improvement in VL and adherence, regardless of which second-stage treatment participants received. Due to contraction of sample size compared to our original plan, we do not plan to adjust α for multiple of testing. In addition to PH1, for those subjects we have VL suppression data available we would perform similar LME to test for its significance. We also expect some subjects with complete VL data and many with partial VL data for

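### The primary mixed models name clinical site, age and gender as strata, but randomisation used mode of infection and then first-stage arm and response; the PH2 group and the site rule also need one clear statement each (minor)

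*SAP*

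**What the plan says.** **Models.** SAP 1.2.1 gives each linear mixed model a random intercept and slope, with fixed effects for intervention group and time "as well as the stratification variables: clinical site, age, gender". Protocol 16.0 (Quantitative Analysis Plan) has the same list. The decision rule for both hypotheses is the group-by-time interaction.

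**Stage 1 randomisation.** Protocol 5.0: "Stratification is based on method of contraction: Perinatal vs Behavioral (and other". SAP 1.1: "This step will use stratified randomization in permuted blocks to achieve balance in distribution of behaviorally and perinatally infected youth". Race, ethnicity and gender are only monitored.

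**Stage 2 randomisation.** Protocol 5.0: "At the 3-month follow-up, a second stratified randomization will occur in blocks with 8 possible intervention trajectories as follows". The list that follows splits participants by first-stage arm and response. Protocol 16.0 and SAP 1.1 add: "we will only maintain the balance within each first stage treatment outcome when randomizing at the second stage".

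**Other route for a covariate.** SAP 1.1: "If a baseline variable is not balanced between groups and is correlated with the dependent variable" (r > .30), it is added.

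**Group term.** SAP 1.2.1 says "All the primary analyses will be based on initial assignment to groups, using the ITT principle" and gives the purpose of the mixed model as "to determine which of the first-stage intervention, CPS or SMS, is associated with the most improvement in VL and adherence". Hypothesis 2 in SAP 1.2 is a second-stage contrast: non-responders given CPS with incentives against those given SMS with incentives.

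**Site.** SAP 1.2.1 puts site in every model and adds site-by-group if it is significant at 0.05. SAP 1.2.3 and the protocol's Site Clustering Effects paragraph test the site-level variance. They drop to a two-level model if it is not significant, and otherwise use dummy codes together with a third level.

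**The concern.** A model that claims to adjust for the stratification factors should contain the factors that were used. Here the named ones were not used and the used ones are not named. Leaving out a prognostic factor that was balanced by design overstates the standard error of a simple comparison, so the test becomes conservative and some power is lost.

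Two further gaps leave the analyst to choose. SAP 1.2.1 never says what the group term means in PH2, where non-responders from both first-stage arms are pooled. And site has two treatments that are not reconciled. With about 32-65 evaluable participants in PH2, the model should be settled before the data are seen.

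**Working it through.** **1. Factors side by side.**

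| Model | Randomisation factors | Already handled | Missing |
|---|---|---|---|
| PH1 (first-stage CPS vs SMS) | mode of infection | none | mode of infection |
| PH2 (CPS-I vs SMS-I, per SAP 1.2) | first-stage arm, response | response, by restriction to non-responders | first-stage arm |

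Site, age and gender appear in neither randomisation. The SAP 1.1 covariate rule needs imbalance, which stratification is designed to prevent, so it is unlikely to restore mode of infection.

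**2. The plan's power figure.** SAP 1.2.4 claims at least 80% power at effect size 0.55 with 60 per group, two-sided alpha 0.05 and 10% attrition. Per group, n = 2(1.960 + 0.842)²/0.55² = 51.9, so 52. With 60 × 0.9 = 54 per group, the noncentral t (106 df) gives 0.808. The claim reproduces for the two-group comparison and does not depend on the covariates.

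**3. First-stage endpoint comparison with the stratum omitted.** The documents give neither the prognostic strength of mode of infection nor the perinatal share q, so R², the share of outcome variance that the stratum explains, is assumed.

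- Type I error = 2[1 − Φ(1.96/√(1 − R²))].
- Adjusted power uses effect size 0.55/√(1 − R²) with 105 df.
- Stratum difference needed, in within-stratum SD = √{[R²/(1 − R²)]/[q(1 − q)]}.

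| R² | Type I, unadjusted | Adjusted power | Simulated power, unadjusted vs adjusted (20,000 runs) | Difference needed at q = 10%, 20%, 30% |
|---|---|---|---|---|
| 2% | 0.0477 | 0.816 | 0.810 vs 0.815 | 0.48, 0.36, 0.31 |
| 5% | 0.0443 | 0.828 | 0.815 vs 0.827 | 0.76, 0.57, 0.50 |
| 10% | 0.0388 | 0.847 | 0.818 vs 0.845 | 1.11, 0.83, 0.73 |

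The gain from adjusting is 0.5, 1.2 and 2.7 points.

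**4. Group-by-time test.** Assumptions: five visits, random intercept and slope, within-subject correlation 0.3 and 0.5 (the ends of the range in protocol 16.0), slope variance 0.1 and 0.4, R² 2-10%. Omitting the stratum main effect changes the standard error by 0% with complete data and by less than 0.5% with 30% dropout, in PH1 and PH2. A separate simulation (108 completers, 8,000 runs) put the stratum effect on slope instead. With stratum-by-time omitted, type I error was 0.047, 0.040 and 0.028 for slope differences of 0.1, 0.2 and 0.3 per visit, against 0.049 with none.

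**5. Size of PH2.** For a responder rate p of 0.4-0.7 (the SAP 1.2.4 table), 120(1 − p) = 72-36. Times 0.9 this is 65-32 evaluable, or about 16-8 per first-stage by second-stage cell.

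**6. PH2 read literally as first-stage CPS vs SMS among non-responders.** Model: latent normal month-3 response, correlation 0.3-0.5 with the endpoint, no second-stage effect and no lasting first-stage effect, 10% attrition.

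| Response, SMS/CPS | Bias against CPS (SD) | Rejection rate |
|---|---|---|
| 40/40 | 0 | 0.050 |
| 40/50, 50/60 | 0.05-0.09 | 0.054-0.062 |
| 40/60, 50/70 | 0.10-0.20 | 0.065-0.097 |
| 40/70 | 0.16-0.28 | 0.082-0.153 |

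**The case against.** The strongest reply is that nothing decisive changes. Both hypotheses are decided by group-by-time, and step 4 shows that a stratum main effect leaves that test almost untouched. The type I and power figures in step 3 concern a single-visit comparison and rest on an assumed R², whose upper end needs a large difference between strata. This stands, and it is why the point is minor. A reader might infer that the primary tests are invalid or inflated. The documents do not support that, because omitting a balanced stratum errs on the conservative side.

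A reader might also infer that PH2 is planned as a biased, non-randomised comparison. SAP 1.2 speaks against this by stating hypothesis 2 as a second-stage contrast. The purpose sentence refers to the primary aim in the singular, and the initial-assignment sentence follows directly on the first-stage tests and may be ordinary intention-to-treat wording. Under the equal responder rates assumed in SAP 1.2.4, the bias in step 6 is zero. But the initial-assignment sentence covers all primary analyses without limit, so a clarification is still needed.

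The two PH2 complaints cannot both apply. First-stage arm is missing only if group means the second-stage assignment. The biased contrast arises only if group means the first-stage assignment, and then first-stage arm is already in the model.

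On site, SAP 1.2.3 plans a group identifier for every participant, so it would be wrong to say that those recruited online have no code. A two-level model can also keep site as a fixed effect. What remains is that the identifier's value for people without a referring site is not stated, and that the conditional dummy codes in 1.2.3 do not fit the unconditional site term in 1.2.1.

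**Conclusion.** The stratum list is wrong as written in both documents. Mode of infection is missing from PH1 and, on the likely reading of its group term, first-stage arm is missing from PH2.

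The effect is small. There is no bias and no type I inflation. The unadjusted first-stage endpoint test is mildly conservative, at about 0.048-0.039 for an assumed R² of 2-10%, and adjusting gains about 0.5-3 points of power. The group-by-time test is essentially unchanged unless the stratum affects slope.

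The undefined PH2 group and the two site treatments are ambiguities to close. The rejection rates in step 6 belong to the less likely reading and arise only if response rates differ between arms, so they do not raise the severity. Minor.

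**What to change.** In SAP 1.2.1 and 1.2.3, and in the matching paragraphs of protocol 16.0:

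1. Replace the stratum list with the true randomisation factors as fixed effects: mode of infection in PH1, first-stage arm in PH2. Stratum-by-time terms are optional. Adjust the first-stage endpoint comparison for mode of infection by regression, logistic for the rate and linear for the continuous measure. The estimates then pool under the Rubin's rules already planned in SAP 1.2.5. A Cochran-Mantel-Haenszel test would not fit that pooling directly.
2. State that the PH2 group is the second-stage assignment, CPS-I versus SMS-I. Limit the initial-assignment sentence and the first-stage purpose sentence to PH1.
3. Keep age and gender as prespecified covariates, not strata.
4. State one site rule, fixed in advance, that says what value the planned group identifier takes for participants without a referring site and whether site-by-group falls under the rule.

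The cost is wording plus one fixed-effect parameter per model, using data already recorded for randomisation. Cells may be sparse: at an assumed 10% perinatal share, stage 1 would have about 60 × 0.10 = 6 perinatally infected participants per arm, and PH2 about 3-6 in all.

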1.2 Quantitative Analysis Plan

Original Primary Hypotheses: 1. Youth randomized to CPS will have significantly greater VL suppression (primary outcome) and self-reported medication adherence (secondary outcome) at 24 weeks than those in SMS group. 2. Non-responders randomized to CPS with incentives will have significantly greater VL suppression (primary outcome) and self-reported adherence (secondary outcome) than those randomized to SMS with incentives.

Original Secondary Aims: a) Conduct an exploratory evaluation of tapering the intensity of CPS and SMS (among responders) vs termination after completion of the 24 week intervention to determine if this improves the durability of intervention effects; b) Explore the relative efficacy of the individual intervention sequences embedded within the SMART design for responders and non-responders; and c) Describe moderators of the treatment effect, including demographics, mode of infection, substance use, and mental health. [NOT COMPLETED DUE LOW RENTENTION]

Updated Primary Outcome: Originally, we plan to treat VL suppression as our primary outcome for both co-primary hypothesis. Primary end-point for H1 was at 24 weeks when the proximal outcome was used to determine responder status, while for H2 the Distal outcome was at end of 12 months (or 72 weeks). Due to the difficulty in collecting viral load we proposed to change the primary outcome to a combination of VL suppression and self-reported adherence (SRA). Primary end-points for both co-primary hypothesis is now at 48 week.

Rationale of new definition of Primary Outcome: Since the VLS data may not be available for a significant number of subjects, we plan to use SRA as an additional primary outcome. The usefulness and appropriateness of the usage of these two depends upon the concordance of two measures. To determine that for those subjects we have both VLS and SRA data available, we will first construct a 2×2 contingency table and conduct a chi-square test of association. If they agree on 80% or more cases we will proceed to define (and analyze) the primary outcome as following:

- 1) For any data collection point and randomization event, if VLS data is available it will be used as primary outcome. When VLS data is not available, SRA will be used as primary outcome. This composite definition will be used as primary outcome and will have sufficient power based on hypothesized effect size.

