1.2.4 Sample Size and Power

Sample Size and Power. Statistical power analyses examined the sample size requirements to detect greater than chance group differences on primary outcome (PH1 and Ph2). We have used Susan's formula with a total sample size of 120.

<http://people.seas.harvard.edu/~samurphy/papers/APPProof.pdf>

| Power Table | | | |
|--------------------|------------|------------|-----------------------------|
| ES | p | N | N(10% attrition adjustment) |
| 0.55 | 0.4 | 86 | 96 |
| | 0.5 | 104 | 116 |
| | 0.6 | 130 | 144 |
| | 0.7 | 174 | 192 |
| 0.6 | 0.4 | 74 | 80 |
| | 0.5 | 88 | 98 |
| | 0.6 | 110 | 120 |
| | 0.7 | 146 | 160 |

Alternatively, for the two groups comparison this corresponds to n=60/group. This sample size is sufficient to provide 80% power (or more) for a standardized Effect Size (ES) of 0.55 or more, using a t-distribution for a two tailed test with $\alpha=0.05$, with 10% attrition assuming equal responder rate (p) in both arms.

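### The decision rule for both primary hypotheses tests group-by-time over weeks 0–48, but the stated end-point is week 48 and the stated power is for a two-group t-test

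*SAP*

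**What the plan says.** Three parts of the SAP point to three different primary contrasts.

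- **End-point.** SAP 1.2, on the updated outcome: "Primary end-points for both co-primary hypothesis is now at 48 week".
- **Decision.** SAP 1.2.1: "A likelihood ratio test will examine the incremental contribution of the group by time interaction", and then: "The decision rule for each primary hypothesis calls for rejection of H_0 if this interaction is statistically significant using the Hochberg adjustment". The model is described as follows: "Each LME model will include a random intercept and slope and fixed effects for adherence intervention group, and time". The visits are given inconsistently: "the model will include up to 3 repeated assessments of VL suppression (weeks 0/baseline, 12, 24, 36, 48". Whether time is linear or categorical is not stated.
- **Named primary analysis.** SAP 1.2.1 opens by giving this title to a "comparison of SRA (primary outcome) between the CPS and the SMS group at the end of first stage of randomization", which plays no part in the decision rule.

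The power statement in SAP 1.2.4 follows a table from a SMART sample-size formula: "Alternatively, for the two groups comparison this corresponds to n=60/group" and "This sample size is sufficient to provide 80% power (or more) for a standardized Effect Size (ES) of 0.55 or more". It refers to a t-distribution with two-sided alpha 0.05 and 10% attrition. It does not mention an interaction.

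The only text that ties a slope to an end-point difference is in Protocol 16.0 (Sample Size and Power). It was written for the superseded plan of 190 participants, and the SAP does not restate it.

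**The concern.** A test of group-by-time asks whether the arm difference changes over the whole follow-up. A week-48 end-point asks whether the arms differ at week 48. With linear time, visits before the midpoint enter the slope with negative weight, so a benefit of cell phone support (CPS) at week 12 counts against CPS.

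That matters for the first hypothesis (PH1) because of the design in Protocol 4.0 and 5.0. First-stage contact lasts three months. Non-responders from both first-stage arms are then re-randomised between the same two incentive options. All responders are in standard care from month 6. Given response status, first-stage arm changes assigned contact only for tapered responders in months 3–6, and for nobody after month 6. An arm difference that keeps growing in a straight line to week 48 is therefore doubtful.

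At stake is the rejection rule for both primary hypotheses. It can miss a week-48 difference or reject when there is none, and a reader cannot tell which primary result governs.

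**Working it through.** **Inputs.** 60 per group, effect size (ES) 0.55, two-sided alpha 0.05 and 10% attrition (SAP 1.2.4), so 60 × 0.9 = 54 per arm. Visits at weeks 0, 12, 24, 36, 48 (SAP 1.2.1). Within-subject correlation (ICC) 0.30, 0.40, 0.50 (Protocol 16.0). Assumptions: continuous outcome, linear time, no slope variance, and the shapes of the arm difference D(t), since the documents give none.

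**The plan's own figure.** Two-sample t-test at ES 0.55: 84.8% power at 60 per arm and 80.8% at 54. The normal-approximation size is 52 per arm, 104 in total, and 104/0.9 = 116. This reproduces the stated 80% and the 104/116 row of the table, for a two-group comparison.

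**What the interaction estimates.** Fitted slope over 48 weeks = Σ a(t)D(t), where a(t) = 48(t − 24)/Σ(t − 24)². With Σ(t − 24)² = 1440, the weights are −0.8, −0.4, 0, +0.4, +0.8.

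Its standard error is 4 × √[2(1 − ICC)/(10 × 54)], or 0.204, 0.189, 0.172 for ICC 0.30, 0.40, 0.50. Power follows from z = slope/SE against 1.96.

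| Arm difference at weeks 0/12/24/36/48 | Slope over 48 weeks | Interaction | Week-48 t-test |
|---|---|---|---|
| Linear: 0, .14, .28, .41, .55 | 0.55 | 77–89% | 81% |
| Sustained: 0, .55, .55, .55, .55 | 0.44 | 58–72% | 81% |
| 90% kept per visit: 0, .55, .50, .45, .40 | 0.28 | 28–37% | 54% |
| Week 12 only: 0, .55, 0, 0, 0 | −0.22 | significantly negative in 19–25% | 5% |

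Worked line, sustained effect: 0.55 × (−0.4 + 0 + 0.4 + 0.8) = 0.44. Then z = 0.44/0.204 = 2.16 at ICC 0.30 and 0.44/0.172 = 2.56 at ICC 0.50, giving 58% and 72%.

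Simulated likelihood-ratio tests with random intercept and slope gave 55–70% (sustained), 76–88% (linear) and 17–22% (week 12 only, negative). A random-slope SD of 0.5 over 48 weeks lowers the closed-form figures to 50–61% for a sustained effect and 69–80% for linear growth.

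**Fitted lines.** The sustained effect is fitted as 0.22 at week 0 and 0.66 at week 48, although the true values are 0 and 0.55. The week-12-only effect is fitted as 0.22 at week 0 and 0.00 at week 48.

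**Break-even under decay.** Suppose the effect is full at week 12 and a share r is kept per visit. The slope is zero when −0.4 + 0.4r² + 0.8r³ = 0, so r = 0.657, a loss of about 34% per visit. The true week-48 difference is then 0.55 × 0.284 = 0.16, for which a week-48 t-test has 12.7% power. The threshold depends on the shape:

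- Full effect held from week 12 to week 24, then decay: −0.4 + 0.4r + 0.8r² = 0, so r = 0.50.
- Half-built at week 12, full at week 24, then decay: −0.2 + 0.4r + 0.8r² = 0, so r = 0.31, with a week-48 difference of 0.05.

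**Categorical time.** The interaction becomes a 4-df test. For the week-12-only effect the noncentrality is (54/2) × 0.55² × 0.8/(1 − ICC) = 9.3, 10.9, 13.1. Power is 68%, 76%, 84%, although the arms are equal at week 48.

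**Second hypothesis (PH2).** With 50% non-responders (Protocol 16.0) and equal second-stage allocation (assumed), 108 × 0.5/2 = 27 per arm. For a constant difference from week 24, the slope is 0.55 × (0.4 + 0.8) = 0.66, not 0.55. Interaction power is 63–77%, against 55–63% for a week-48 test adjusted for a prior value, using 0.55/√(1 − ICC²).

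**The case against.** The strongest reply is that the slope is the intended target. Protocol 16.0 powers on it, SAP 1.2.1 describes a differential effect over time, and no text withdraws it. That stands to this extent: the documents do not settle whether the week-48 statement or the rule is the one to change. It does not remove the conflict, and the SAP's power statement still belongs to neither.

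Several stronger readings are tempting and should not be drawn:

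- *That the two nulls coincide only under linear growth from zero.* They do not need it. For a sustained step the slope is zero exactly when the week-48 difference is zero. Linear growth from zero is what guarantees that the numbers are equal. A zero start is not in doubt for PH1, because randomisation gives it in expectation.
- *That a 34% loss per visit is a fixed tipping point.* It moves to 50% or 69% under other shapes. The length of stage 1 is itself unclear: month 3 in Protocol 5.0, after six months in SAP 1.1, and an original 24-week responder point in SAP 1.2. At break-even the week-48 test would usually miss the effect too.
- *That a negative interaction means text messaging (SMS) is better.* In the week-12-only case the fitted arms are equal at week 48 and CPS is never worse.
- *That the decision null can hold while the arms differ at week 48, whatever the coding.* With categorical time and a zero start, the null means no difference at any visit, so this needs linear time.
- *That PH2 has an inflated type I error.* Including visits before the second randomisation blurs interpretation but does not inflate error.

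In the week-12-only case the end-of-first-stage comparison would have 81% power in its continuous form, if stage 1 lasts three months. The negative slope would not be reported alone, although only the slope decides.

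**Conclusion.** The point holds as a mismatch between the end-point, the decision rule and the power statement. It is certain on the text. Its numerical size rests on the assumptions listed with the calculation.

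The practical loss is clearest when a first-stage effect arrives early and is kept or fades slowly: about 9 to 23 percentage points for a sustained effect (81% against 58–72%) and 17 to 26 points with 90% kept per visit (54% against 28–37%). The opposite error, rejecting without a week-48 difference, is largest in the extreme week-12-only case. The interaction is not uniformly weaker, since under linear growth it matches or exceeds the week-48 test over most of the ICC range. For PH2 the harm is limited to interpretability.

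**What to change.** Name one target and use it in SAP 1.2, 1.2.1 and 1.2.4.

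- **If week 48 is the target:** test the CPS–SMS difference at week 48 from a model with categorical visits and baseline as covariate (logistic mixed model or GEE if the outcome is binary). Report the end-of-first-stage, other-visit and slope contrasts as supportive.
- **If the slope or the end of the first stage is the target:** change the end-point statement in SAP 1.2, state how time is coded, and restate the power for that test.
- **PH2:** use visits after the second randomisation, adjusted for the value at that randomisation and for first-stage arm.
- **Reconcile** the count of three assessments with the five listed weeks in SAP 1.2.1, and the timing of the second randomisation in Protocol 5.0 with that in SAP 1.1.

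The cost is SAP wording, reprogramming and a few degrees of freedom. There is a statistical price too. A week-48 contrast has low power if the effect wanes: with 75% kept per visit the week-48 difference is 0.23 and power is 22%. It can also fall short of the slope, at 81% unadjusted against 89% under linear PH1 growth at ICC 0.50, and for a constant PH2 effect as shown above.
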